## 1.0 Background

Asthma is characterized by chronic airway inflammation, repeated episodes of reversible airway obstruction and airway hyper-reactivity. Airway inflammation and clinical symptoms of asthma are most often initiated by IgE-mediated responses following exposure to environmental allergens. Inflammatory cell recruitment into the lungs and airway hyper responsiveness are key components of the allergen-induced inflammatory response, which results from the interaction of resident airway cells and inflammatory cells that release local mediators. Patients with severe, recurrent asthma also have remodeling of the airway wall with increased airway smooth muscle, increased inflammatory cells and collagen deposition.

For many decades, corticosteroids have been used to control airway inflammation, while  $\beta$ -adrenergic bronchodilators have been the primary treatment for bronchoconstriction. Although these therapies are effective for the vast majority of asthmatics, they are limited by high cost, poor adherence, and increasing concern about long-term adverse effects. The FDA has issued a black-box warning linking long-acting  $\beta$ -adrenergic bronchodilators to asthma deaths, and other studies have linked corticosteroids to fracture risk and growth retardation. Recently introduced therapies that focus on inhibiting a single component of the allergic inflammatory response, such as anti-IL-5 or anti-IL-13 antibodies, have had limited efficacy. Thus, there is a compelling need for new, safe and effective approaches to asthma treatment, particularly in children with severe asthma, where there is generally a lifelong burden of disease, use of medications, and accounts for the majority of health care expenditures among all children with asthma. **The development of a therapeutic approach that could reduce both airway responsiveness and airway inflammation would be an important advance in the treatment of asthma.**

During the previous funding period of this project, our laboratory demonstrated that chronic mechanical strain imposed on the airways *in vivo* using continuous positive airway pressure (CPAP) results in a dramatic reduction in airway reactivity *in vivo* in mice, ferrets and rabbits. Lungs, airways and airway smooth muscle (ASM) tissues isolated from CPAP-treated animals studied *in vitro* exhibited lower responsiveness to bronchoconstrictors. We also observed this suppression of airway responsiveness by chronic mechanical strain in a rabbit model of allergic asthma. These animal studies led to a small clinical trial in which adults with asthma were treated with nocturnal CPAP for 1 week. CPAP caused a significant reduction in airway reactivity in these patients. This novel approach for treating airway hyper-reactivity is currently being evaluated in a NIH multi-center Phase II clinical trial of adults with mild to moderate asthma (U01 HL108730).

We now propose to determine the efficacy of chronic mechanical strain as an inhibitor of airway inflammation. Our preliminary studies have demonstrated that chronic mechanical strain can suppress the responses of airway tissues to allergic inflammatory stimuli and suppress the activation of signaling molecules involved in these responses. Based on these studies, **we hypothesize that chronic mechanical strain will inhibit signaling processes in airway tissues that lead to airway inflammation, hyper-reactivity and remodeling**. We propose a novel molecular mechanism for the inhibitory effects of chronic mechanical strain on the responses of ASM to inflammatory stimuli. Anti-inflammatory agents such as corticosteroids remain the primary treatment for severe chronic asthma. The consequences of long term steroid therapy can be extremely deleterious, particularly in children, for whom steroids can have a significant adverse impact on growth and development. Our proposed study will provide the basis for a new non-pharmacologic therapy for the control of asthma that may be particularly important for the treatment of children with severe steroid-dependent disease. We will determine whether mechanical strain, as delivered using CPAP, is an effective therapy for suppressing airway hyper-reactivity and inflammation in pediatric subjects with severe asthma. **The concept that a non-pharmacologic therapy may play such a pivotal role in suppressing ASM contraction, inflammation and tissue remodeling is novel and exciting**. Furthermore, elucidation of the molecular mechanisms by which strain suppresses inflammatory signaling pathways could also provide a basis for the development of new pharmacologic targets for asthma therapy.

**Pathophysiology of airway inflammation in asthma.** Th2 cytokines derived from CD4+ T lymphocytes play a pivotal role in the airway pathology associated with asthma. The structurally related Th2 cell derived cytokines interleukin (IL)-4 and IL-13 stimulate allergic and eosinophilic inflammation as well as

epithelial and smooth muscle changes, and they are widely recognized as mediators of allergen-induced airway hyperresponsiveness and airway remodeling. Th2 cytokines can induce airway hyper-reactivity without inflammatory cell recruitment which indicates that many of the pathophysiologic effects of allergic inflammation in asthma result from the direct actions of IL-4 or IL-13 on airway cells. The incubation of ASM with IL-

[figure not shown]
13 or IL-4 *in vitro* causes ASM hypercontractility, inhibits relaxation to isoproterenol and stimulates release of the eosinophil chemo-attractant eotaxin and IL-5. The cytokines secreted by ASM and other airway cells have paracrine effects on inflammatory cells and thus contribute to airway inflammation.

Phenotypic alterations in airway cells induced by the direct actions of cytokines may be a primary mechanism for airway remodeling in asthma. Changes in gene expression induced by IL-13 or IL-4 have been demonstrated in airway cells including ASM, fibroblasts and airway epithelial cells. Both IL-4 and IL-13 activate signaling pathways that regulate cell growth and proliferation as well as the expression of responsive genes. The direct stimulation of resident airway cells with inflammatory cytokines *in vitro* stimulates cell growth and proliferation and the secretion of matrix proteins. *In our previous animal studies, we evaluated the effects of chronic mechanical strain on the physiologic responses of ASM tissues to inflammatory mediators in vitro, and on airway inflammation and remodeling in vivo using murine models of asthma.*

### Molecular mechanisms for the direct effects of inflammatory cytokines on ASM cells.

IL-4 and IL-13 both signal through a heterodimeric receptor complex that consists of an IL-4R $\alpha$  chain and an IL-13R $\alpha$  chain (Fig.1). In response to stimulation, the IL-4/IL-13 receptor subunits associate with Janus Kinases (Jak) that phosphorylate the IL4R $\alpha$  and IL13 receptor side chains, activating two distinct signaling proteins that bind to the phosphorylated IL-4R $\alpha$  receptor side chain: insulin receptor-2 (IRS-2) and "signal transducer and activator of transcription 6"(STAT6). IRS2 activates the PI3 kinase-dependent protein kinase Akt, a regulator of cell growth and hypertrophy, as well as ERK1/2 MAP kinase and other MAP kinases. phosphorylation by Jak, activated STAT6 dimerizes and migrates to the nucleus where it initiates the transcription of IL-4/IL-13 responsive genes. Stimulation of ASM cells or tissues by IL-4/IL-13 *in vitro* results in the phosphorylation of Akt, ERK1/2 and STAT6, the synthesis and secretion of eotaxin and IL-5, and suppresses the expression of smooth muscle phenotype-specific proteins (Figs.1,4-6). Our previous studies and preliminary data have shown that chronic mechanical strain suppresses the activation of Akt and ERK, and that strain inhibits eotaxin secretion and IL-13-mediated gene transcription (Figs. 5,6,9).

Fig 1. Signaling Pathways Activated by IL-13/IL-4 Receptor

### Chronic mechanical strain suppresses airway responsiveness and ASM contractility.

[figure not shown]
Mechanical strain of the lungs during breathing has an important role in reducing airway responsiveness. Deep inspirations and tidal breathing decrease airway responsiveness acutely in healthy adults and animals and their absence increases airway responsiveness. Similar effects of mechanical strain have been observed in isolated airway segments and trachealis smooth muscle strips studied *in vitro*, demonstrating that the effects of mechanical strain on airway reactivity reflect its direct effects on ASM. Although the effects of deep inspiration on airway reactivity are short-lived, these observations suggest that mechanical strain could be a useful approach for suppressing airway hyperresponsiveness.

We initially explored the effects of imposing mechanical strain on the airways for prolonged time periods to determine whether it could cause a longer term reduction of airway responsiveness. Chronic mechanical strain for 1-2 days applied to bronchial segments or tracheal muscle strips *in vitro* resulted in a decrease in their contractile responsiveness to ACh as assessed subsequently under unstrained conditions. These results suggest that chronic strain can induce persistent alterations in the functional properties of the ASM tissues.

We subsequently tested the effects of chronic strain *in vivo* by applying CPAP to rabbits and ferrets for periods of 4 days to 2 weeks and found that CPAP suppressed airway reactivity to ACh *in vivo*. Lopes,

airway segments and tracheal smooth muscle tissues excised from the lungs of these CPAP treated animals also exhibited reduced contractility *in vitro*. The effects of chronic mechanical strain on airway reactivity were persistent and could be detected for at least 24 hours after CPAP. In addition, the continuous use of CPAP was not necessary for it to be effective: limiting CPAP to nocturnal periods for 4 days in rabbits was similarly effective in reducing airway responsiveness (Fig. 2A). We also tested the efficacy of chronic mechanical strain at reducing airway hyperresponsiveness in the presence of allergic airway inflammation. In Ova-sensitized and challenged rabbits continuous CPAP administered for 4 days was effective at suppressing airway reactivity (Fig 2B). We recently extended this study to human asthmatics: Adults with stable asthma and normal spirometry used nocturnal CPAP for 7 days. CPAP resulted in a significant decrease in airway reactivity while a Sham-treated group of asthmatics had no significant change in airway reactivity.

**Fig. 2. CPAP Reduced Airway Reactivity in Rabbits**

[figure not shown]

### Effects of chronic mechanical strain on ASM phenotype and its responses to inflammatory mediators.

ASM cells in culture modulate their properties between a synthetic and differentiated phenotype. Integrin proteins are widely recognized to be important regulators of cell phenotype, and can mediate transitions in the phenotypic status of cells in response to changes in the composition or stiffness of the extracellular matrix. Changes in ECM have been shown to modulate the secretion of eotaxin by ASM cells in culture in response to stimulation with IL-13.

Our data indicate that mechanical strain imposed on ASM tissues is a potent stimulus for regulating the phenotype and synthetic status ASM tissues. When we imposed chronic mechanical strain on ASM tissues *in vitro*, the activation of pathways mediated by PI3-kinase dependent Akt were suppressed while the expression of smooth muscle phenotype-specific proteins was potentiated (Fig. 4). We confirmed this effect on the airways of mice subjected to chronic mechanical strain *in vivo*: the activation of Akt was significantly depressed in animals subjected to prolonged high mechanical strain using PEEP as compared with control-treated animals (Fig. 13C). Because Akt is a critical mediator of pathways activated by inflammatory stimuli such as IL-13, we hypothesized that mechanical loads would suppress the inflammatory responses of ASM to local mediators and might thereby mitigate airway inflammation (Fig.4).

**Fig 4. Interaction of IL-13/IL-4 Receptor with Integrin Adhesome Signaling**

We performed studies on ASM tissues *in vitro* to evaluate the effects of mechanical strain on the responses of ASM tissues to stimulation with the inflammatory cytokine IL-13. The administration of IL-13 to ASM tissues *in vitro* stimulated the synthesis and expression of the chemokine, eotaxin, and suppressed the expression of smooth muscle phenotype-specific proteins (Figs. 5,6). Subjecting ASM tissues to mechanical strain suppressed IL-13 stimulated eotaxin synthesis and secretion and potentiated the expression of smooth muscle specific proteins, promoting the differentiated phenotype. **Thus, while IL-13 promotes chemokine synthesis and the synthetic phenotype of ASM, mechanical strain opposes this effect, suppressing IL-13 stimulated eotaxin synthesis and promoting the differentiated phenotype.** (Fig. 4)

Our studies have also established the role of integrin signaling in the regulation of ASM differentiation and mechano-sensitive signaling to the nucleus. We found that integrin-linked kinase (ILK), a multi-domain  $\beta$  integrin-binding protein kinase that regulates Akt, is a critical upstream regulator of signaling pathways that regulate the synthetic and differentiation functions of ASM tissues. ILK forms a stable heterotrimeric complex with PINCH, an adaptor protein, and  $\alpha$ -parvin, which binds to actin filaments. ILK also binds directly to  $\beta$  integrin proteins and to the mechano-sensitive adhesome protein paxillin, and paxillin binding is necessary for the localization of ILK to integrin adhesomes. ILK regulates the PI3 kinase-dependent

activation of Akt. We found that Akt activation inhibits the transcriptional regulator, serum response factor (srf) in ASM, thereby suppressing the expression of smooth muscle phenotypic proteins. Mechanical loads inhibit the ILK-dependent activation of Akt, thus promoting the differentiated phenotype (Fig. 4). Our preliminary data also show that the ILK complex also plays a critical role in regulating the mechanosensitivity of eotaxin synthesis in response to the stimulation of ASM with IL-13 (Fig. 10).

### Summary.

We have shown that chronic mechanical strain suppresses allergen-induced hyper-responsiveness *in vivo* in animal models of asthma and the effectiveness of nocturnal CPAP at reducing airway hyper-reactivity in adults with mild-moderate asthma. Our studies of ASM tissues indicate that mechanical strain is sensed and transduced by integrin adhesomes to signaling pathways that regulate the synthetic and differentiation status of ASM. Our proposed studies will use *in vitro* models to assess the effects of strain on the inflammatory responses of ASM tissues (SA #1), will evaluate the suppression of airway inflammation by chronic strain in murine models of asthma (SA #2), and will **test the efficacy of mechanical strain as therapy to suppress airway inflammation and hyper-reactivity in children with severe asthma (SA #3)**.

[figure not shown]
#### **SPECIFIC AIM #3: DETERMINE WHETHER CPAP SUPPRESSES AIRWAY HYPER-REACTIVITY AND AIRWAY INFLAMMATION IN CHILDREN WITH SEVERE ASTHMA.**

**RATIONALE.** Whereas some children with asthma have intermittent symptoms that are improved with short-acting bronchodilators, many have persistent symptoms requiring daily treatment with inhaled corticosteroids. Children with severe asthma often have ongoing symptoms, airway inflammation and hyper-reactivity despite treatment with high doses of inhaled corticosteroids. They are at high risk for asthma exacerbation requiring systemic corticosteroids, emergency room visits and hospitalization. Children with severe asthma are often highly atopic with increased peripheral blood eosinophilia, aeroallergen sensitivity, elevated serum IgE concentrations, elevated eNO, and eosinophilia in induced sputum and BALF. A novel non-pharmacologic treatment that suppresses airway hyper-reactivity and inflammation in children with severe asthma could provide a significant advance in the therapy for these difficult to treat patients. **We hypothesize that chronic mechanical strain will suppress airway reactivity and inflammation in children with severe asthma.** In SA #3 we will determine whether the use of nocturnal CPAP for 1 month in children with severe asthma suppresses airway reactivity as assessed by bronchial challenge, and airway inflammation by induced sputum.

**PRELIMINARY DATA.** Our recent study of adults with mild-moderate clinically stable asthma demonstrated that treatment with nocturnal CPAP for 1 week decreased airway reactivity (increase in PC20) compared to a Sham-treated group. These results provided the pilot data for our current NIH phase II multi-center clinical trial designed to assess the effectiveness of using nocturnal CPAP to suppress airway reactivity in subjects with mild-moderate asthma. However, this trial is restricted primarily to adult patients who may not be steroid-dependent and are less likely to have persistent airway inflammation or exhibit airway remodeling. Therefore we plan to evaluate children with severe asthma, as CPAP therapy may be particularly beneficial to this group. Our study will also assess airway inflammation which is not included in previous or ongoing clinical trials.

**Fig 16**

## 2.0 Inclusion/Exclusion Criteria

### SUBJECT RECRUITMENT

#### Inclusion Criteria:

1. Children 8–17 yrs olds with severe asthma (N=120) will be recruited from the Pediatric High Risk Asthma Clinic and Pulmonary Clinics at Riley Hospital for Children at Indiana University Health.
2. Severe asthma will be defined by the need for medication therapies following steps 4-6 according to the National Institutes of Health's Asthma Care Quick Reference, September 2012 or high dose of inhaled corticosteroids.
3. Children on a stable regimen of asthma medications for at least 8 wks prior to enrollment without systemic corticosteroids for >4 wks will be eligible.

#### Exclusion Criteria:

1. Obese ( $>95\%$  predicted BMI).
2. Congenital heart disease or chronic lung disease.
3. History of pneumothorax.
4. Inability to perform pulmonary function testing.
5. Oxygen saturation  $<93\%$ .
6. FEV1  $<70\%$  predicted.
7. PC20  $\geq 16$  mg/ml of methacholine.

## 3.0 Enrollment/Randomization

### TREATMENT:

1. Nocturnal CPAP (8-12 cmH2O) or Sham (0 cmH2O).
2. Subjects will be randomized to use CPAP or Sham CPAP at night for a total of 28 days (+/- 3 days) with a minimum of 4 hrs/night for at least 5 days/wk. If patient is having asthma symptoms at time of final visit, treatment may be extended up to 14 additional days. If patient receives oral steroids at any time during treatment with nocturnal CPAP, the final visit will be extended to at least 21 days (3 weeks) after the last dose of oral steroid was given. Adherence to the use of CPAP will be checked by having the patient mail the SD data card from their machine to the Investigator on day 7 and day 14 of CPAP usage and by downloading the data at the time of the final visit. Adherence and tolerance of CPAP will be evaluated by periodic phone calls and documented daily calendar diary with hours of use.

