## 4.0 Study Procedures:

1. **Spirometry:** Spirometry will be performed after withholding bronchodilators. Forced vital capacity (FVC) and forced expiratory volume in 1 second (FEV1) will be measured using ATS guidelines.
2. **Airway Reactivity assessed by MCh Bronchial Challenge:** Testing will use the 5 breath dosimeter protocol recommended by ATS. Following inhalation of saline, MCh will be inhaled in quadrupling concentrations starting with 0.0625 mg/ml and continuing until the MCh concentration required for FEV1 to decrease by 20% from baseline (PC20) is achieved or a maximum MCh concentration of 16 mg/ml is inhaled.
3. **Airway Inflammation assessed by Exhaled Nitric Oxide (eNO):** eNO will be measured at a constant expiratory flow of 50 ml/s with a chemiluminescence analyzer (NIOX; Aerocrine) using ATS guidelines.
4. **Airway Inflammation assessed by Induced Sputum.** Sputum induction will be performed after MCh challenge and treatment with albuterol to return FEV1 to  $\geq 70\%$  predicted. Sputum will be induced by inhaling increasing concentrations (3 to 7%) of saline at 5 min intervals. Oscillating positive expiratory pressure (PEP) therapy may be used if needed to assist with sputum expectoration in conjunction with

saline treatments for up to 20 min or until an adequate sample is produced. Spirometry is performed after each expectoration to check that the FEV1 has not decreased by >20%, in which case the child would be given bronchodilator and no more hypertonic saline. Sputum will be processed for differential cell counts and supernatants stored at -80°C for subsequent analysis of eotaxin and eosinophil cationic protein.

5. **Asthma Symptom control:** Asthma control will be assessed by using the Asthma Control Test.
6. **Berlin score:** Questionnaire will be used to determine high or low risk status for obstructive sleep apnea.

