## 6.0 Study Withdrawal/Discontinuation

If the parent/guardian chooses to withdraw the subject from the study, then the parent/guardian will inform a member of the research team. At that time, no further testing will be obtained. Samples already obtained from the subject prior to withdrawal will still be included in analysis.

**Management of Increased Asthma Symptoms:** If a subject's asthma symptoms worsen during the course of the treatment period, they will be directed to their pediatric pulmonologist or the High Risk Asthma clinic for management. Any changes in therapy, including controller medications or courses of systemic steroids will be recorded. As the enrolled subjects have severe asthma, one course of systemic steroids in 4 weeks would not be considered unusual and would not trigger withdrawal from the study. However, an inpatient hospitalization or two courses of systemic steroids in the 4 week treatment period will trigger withdrawal from the study

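### The 21-day steroid washout before the final challenge is triggered only by oral steroids, so a single non-oral systemic course without inpatient admission requires no delay

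*Combined protocol and SAP*

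**What the plan says.** Section 3.0 (Enrollment/Randomization), Treatment item 2, sets the treatment period "for a total of 28 days (+/- 3 days" and gives two reasons for a later final visit.

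- **Steroid use (required).** "If patient receives oral steroids at any time during treatment with nocturnal CPAP, the final visit will be extended to at least 21 days" after the last oral dose. The sentence mentions nocturnal CPAP, but in context it covers both arms.
- **Symptoms at the final visit (optional).** In that case "treatment may be extended up to 14 additional days". This does not depend on steroid use.

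Elsewhere the protocol uses the wider term, systemic:

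- Section 2.0, Inclusion Criteria item 3: children "without systemic corticosteroids for >4 wks will be eligible".
- Section 6.0, recording: "Any changes in therapy, including controller medications or courses of systemic steroids will be recorded".
- Section 6.0, withdrawal: "an inpatient hospitalization or two courses of systemic steroids in the 4 week treatment period will trigger withdrawal from the study". The same section keeps a child with one systemic course in the study and does not restrict the route.

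The primary outcome (section 7.0) is the change in logPC20 after 4 weeks, analysed by ANCOVA adjusting for baseline PC20. The sputum outcome comes from the same visit: "Sputum induction will be performed after MCh challenge" (section 4.0, item 4).

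**The concern.** The 21-day rule shows that the investigators regard recent steroid exposure as a reason to postpone the final tests. Nothing in the protocol explains why exposure by injection or infusion should be treated differently. The Specific Aim #3 rationale says of these children: "They are at high risk for asthma exacerbation requiring systemic corticosteroids, emergency room visits and hospitalization". A course given wholly by a non-oral route in an emergency department or clinic is therefore possible.

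A child with such a course could have the final methacholine challenge and sputum induction on the normal schedule, within days of the dose. The measured rise in PC20 or fall in eosinophils could then partly reflect the steroid. The planned ANCOVA adjusts only for the baseline value, so it would not remove this.

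**Working it through.** **1. Which courses escape the rule**

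| Event during treatment | Withdrawal (6.0) | Required 21-day delay (3.0) |
|---|---|---|
| Inpatient hospitalization | Yes | n/a |
| Two systemic courses in 4 weeks | Yes | n/a |
| One oral course | No | Yes |
| One course, non-oral then oral | No | Yes, from last oral dose |
| One course, non-oral throughout, no admission | No | **No** |

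Only the last row is uncovered. The symptom extension does not close it, because it is optional and a child who is well after the steroid would not meet its condition.

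**2. Timing**

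The visit window is 28 ± 3 days, that is days 25 to 31. After an oral course the earliest visit is max(25, last-dose day + 21).

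| Last dose, day | 4 | 7 | 10 | 14 | 21 | 28 |
|---|---|---|---|---|---|---|
| Earliest final visit, day | 25 | 28 | 31 | 35 | 42 | 49 |

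For a non-oral course ending on day 21, the visit can stay at days 25 to 31: 25 − 21 = 4 to 31 − 21 = 10 days after the dose.

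**3. The plan's own power figure**

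Inputs from section 7.0: difference 0.41, SD 0.46, 27 completers per arm, 5% type I error (taken as two-sided), two-sample t-test. The noncentral t distribution with 52 degrees of freedom gives power 89.5%, consistent with the stated figure of more than 85%.

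**4. Possible effect on the primary comparison**

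The documents give no frequency p of such courses and no residual rise e in logPC20. Assumed ranges: p = 2% to 10%, e = 0.1 to 0.3.

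- *Balanced between arms.* There is no shift in the difference. SD = √(0.46² + p(1−p)e²) = 0.460 to 0.469, and power is 89.5% down to 88.4%.
- *Net excess of k children among 27 in one arm.* Shift = (k/27) × e, from (1/27) × 0.1 = 0.004 to (3/27) × 0.3 = 0.033, which is 1% to 8% of 0.41. An excess in Sham shrinks the difference, with power 89.0% to 84.0%. An excess in CPAP inflates it, with power 90.0% to 93.5%.
- *Effect fading linearly to zero over 21 days, last doses spread evenly over those 21 days.* The mean effect halves. The shift is 0.002 to 0.017, with power 89.2% to 86.9% for a Sham excess and 89.8% to 91.7% for a CPAP excess.

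**5. How likely an imbalance is by chance**

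For two independent Binomial(27, p) counts, the probability that they differ by 3 or more in either direction is:

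| p | 2% | 5% | 10% |
|---|---|---|---|
| Probability | 2% | 11% | 25% |

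**The case against.** The strongest reply is that this is an editorial matter. *Oral* may simply be shorthand for the one systemic course that section 6.0 expects, and no section mentions intramuscular or intravenous steroids. That may be so, but the text does not say it, the same sentence names the oral route twice, and other sections use *systemic*. If shorthand was meant, the amendment only writes down the intention.

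Several points about size are fair and make the effect smaller:

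- A course ending by day 7 is already 21 days before a day-28 visit. Spreading last doses evenly over 28 days, with linear fade over 21, multiplies the full-effect shift by (21/28) × 0.5 = 0.375. The largest shift is then 0.033 × 0.375 = 0.0125, with power 87.6%.
- Power falls below 85% only if the shift exceeds 0.0277. With 3 excess Sham children that needs an undiminished effect of about 0.0277 × 27/3 = 0.25 or more. The chance of a Sham excess of 3 or more is half the two-sided figure: 1.0%, 5.6% or 12.5%. An excess in CPAP, however, would overstate the treatment effect, so that direction is not harmless.
- Section 2.0 gives N=120, whereas section 7.0 plans 30 per group. With 120 randomised and the same 10% loss (54 per arm), a 3-child excess shifts the difference by (3/54) × 0.3 = 0.017 and power stays above 99%.

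It is also true that systemic courses are already recorded, so affected children could be identified, and that the investigator may use the 14-day extension if symptoms persist. Neither requires a delay. Finally, nothing in the documents shows that 21 days is right for non-oral steroids. That is a reason not to claim more for the fix than consistency with the oral rule.

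**Conclusion.** The gap is real on the text. One systemic course that is non-oral throughout and given without inpatient admission requires no postponement, and the final challenge and sputum induction may follow within days of the dose.

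The expected harm is small. On the assumed ranges the difference moves by at most 0.033 (8% of 0.41), and by about half that or less if the steroid effect fades. Such an imbalance would arise by chance and is not a predictable bias toward either arm. All of this rests on assumed frequencies and residual effects, with 27 completers per arm. The 21-day interval itself is not in dispute. The change is worth considering because it is specific and cheap, not because it threatens the trial's conclusion.

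**What to change.** In section 3.0, Treatment item 2, replace the oral-steroid trigger with wording such as:

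> If a participant in either arm receives systemic corticosteroids by any route during the treatment period, the final visit will take place at least 21 days after the last systemic dose.

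Naming both arms is a clarification only. Add the date of the last systemic dose to the record that section 6.0 already requires. Report by arm the days since the last systemic dose and the days on treatment at the final challenge.

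The cost is one amended phrase and one extra date; no sample-size input changes. The downside is that a few more children are measured later than the planned 4 weeks. A last dose up to day 10 still allows a visit by day 31, while a last dose on day 14, 21 or 28 moves the earliest visit to day 35, 42 or 49. The plan already accepts the same delay after oral courses.
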